3.2 Number of Subjects to be Enrolled

Approximately 36 subjects with T2DM are planned to be enrolled in this study, as follows:

Cohort 1: JTT-662 5 mg or placebo

(9 active: 3 placebo)

Cohort 2: JTT-662 10 mg or placebo

(9 active: 3 placebo)

Cohort 3: JTT-662 20 mg or placebo

(9 active: 3 placebo)

To ensure an adequate number of completers, replacement subjects may be enrolled in the study at the discretion of the Sponsor, as appropriate. Each replacement subject will be assigned the same treatment as the subject that is being replaced.

3.3 Randomization and Treatment Assignments

In each cohort, 12 subjects will be randomized to receive JTT-662 or placebo (9 active: 3 placebo) on Day 1. The randomization code will be prepared by an unblinded statistician or designee using an in house program written in SAS[®], a computer software package.

Eligible subjects will be assigned to a treatment according to the list of subject randomization assignments.

3.4 Blinding of Treatment Assignment

On the morning of Day -1, all subjects will receive a single oral dose of placebo in an unblinded manner, following an overnight fast (for at least 10 hours) and 30 minutes before the start of a standard breakfast. From the morning of Day 1 to the morning of Day 28, all randomized subjects will receive either JTT-662 or placebo QD in a single-blind manner, following an overnight fast (for at least 10 hours) and 30 minutes before the start of a standard breakfast. JTT-662 and placebo tablets will be supplied as unbranded tablets which are identical in appearance.

The pharmacist at the site will be responsible for packaging and dispensing the study drug in order to maintain the blind. The treatment assigned to each subject will not be disclosed to the subject; however, the Investigator and site staff will be unblinded. The treatment codes will be controlled by the site's pharmacy or designee.

The laboratory performing the JTT-662, metabolite and metformin (if analyzed) plasma concentration assessments will be unblinded to facilitate analysis of all samples from the JTT-662-treated subjects and appropriate samples from the placebo-treated subjects.

3.5 Breaking the Blind

Not applicable.

4 ANALYSIS PARAMETERS

4.1 Baseline Parameters

4.1.1 Demographic Parameters and baseline characteristics

Demographic variables include age, gender, ethnicity, race, weight, height and body mass index (BMI) measured at the Screening Visit. Hemoglobin A1c (HbA1c) and fasting plasma glucose (FPG) will be measured at the Screening Visit as part of the inclusion criteria assessments.

4.1.2 Medical History

A complete medical history will be obtained at the Screening Visit. The medical history will include past and present conditions prior to the informed consent form (ICF) signature date. Between the ICF signature date and Day 1, prior to dosing, the Investigator should exercise medical and scientific judgement in deciding whether a medical condition, clinically significant laboratory or assessment finding (e.g., clinically significant abnormalities in 12-lead electrocardiogram [ECG], physical examination, vital signs and laboratory test results that are evidently chronic in nature) could be considered medical history or an adverse event (AE).

4.1.3 Prior and Concomitant Medications

Prior/concomitant medications will be assessed throughout the study for all subjects by the investigator.

The information related to the medication (name of drug, dose, route of administration, duration of administration, reason for initiation of each medication) and/or the procedures (e.g., name[s] of therapy, duration of therapy, reason for initiation) will be recorded.

4.2 Pharmacokinetic Parameters

Blood samples will be obtained according to the schedules summarized in Table 1 through Table 5 for the quantification of JTT-662 in plasma.

If needed, PK plasma samples obtained for JTT-662 analysis from this study may be used for metformin concentration determination. The laboratory performing the metformin concentration determination will be unblinded to facilitate analysis of the plasma samples from the JTT-662-treated subjects.

The actual dosing time and sample collection time will be collected for PK data analysis. In addition, the dose and time(s) of dosing of metformin during the PK collection period will also be recorded.

The PK parameters of JTT-662 will be determined from the plasma concentration-time profiles for all subjects in the PK population. Actual sampling times will be used in all computations involving sampling times. Additional PK parameters may also be estimated from the plasma PK data. The PK parameters will be derived by non-compartmental analysis using Phoenix® WinNonlin® (Version 6.4 or higher) and/or SAS® (Version 9.4 or higher).

For the purpose of PK analysis, concentrations that are below the lower limit of quantification (BLQ) will be treated as zero with the exception that a BLQ value between two positive concentrations will be set as missing. Missing concentrations will be treated as missing from the PK parameter calculations. If consecutive BLQ concentrations are followed by quantifiable concentrations in the terminal phase, those concentrations after BLQ concentrations will be treated as missing. A minimum of 4 consecutive measurable concentration-time data points will be required to perform the PK analysis on an individual subject profile.

The following PK parameters will be calculated from PK profiles.

JTT-662 in plasma:

Parameter	Definition
AUC _{tau}	Area under the concentration-time curve during the dosing interval
CL_F	Apparent oral clearance of drug following extravascular administration (total body clearance)
C _{max}	Maximum concentration
t _{1/2(eff)}	Effective half-life
t _{1/2}	Elimination half-life associated with the terminal slope (λz) of a semi-logarithmic concentration time curve
t _{max}	Time to reach peak or maximum concentration following drug administration
C _{trough}	Trough concentration during multiple dosing prior to next dose
λ_z	Apparent elimination rate constant in the terminal phase by non-compartmental analysis
V _z _F	Volume of distribution during terminal phase (λz) following extravascular administration
AR _{Cmax}	Accumulation ratio of maximum concentration
AR _{AUCtau}	Accumulation ratio of area under the concentration-time curve during a dosing interval
ARCtrough	Accumulation ratio based on trough concentration

In the linear up/log down method of AUC calculation, the linear trapezoidal rule is used any time when the concentration data are not decreasing, and the logarithmic trapezoidal rule is used any time when the concentration data are decreasing. The AUCs, terminal phase half-life $(t_{1/2})$ and effective half-life $(t_{1/2(eff)})$ will be calculated

4.3 Pharmacodynamic Assessments

Postprandial glucose (PPG): Blood samples to assess plasma glucose will be collected according to the schedules summarized in Table 1 through Table 4 and area under the observed effect-time curve from the start of breakfast until the 4-hour time point (AUEC₀₋₄) will be calculated. The PD parameters will be estimated using . Below Limit of Quantification values will be treated as zero for PD parameter estimation. Area under the observed effect-time curve will be calculated using the linear trapezoidal rule.

4.5 Safety Parameters

4.5.1 Adverse Events

Adverse events occurring (initial occurrence or a worsening of a pre-existing condition) after the ICF has been signed and up to the day when the decision to screen fail the subject is made (for screen failure subjects), up to 7 days (for subjects discontinuing the study after dosing on Day -1, but before dosing on Day 1) or 14 days (for subjects discontinuing the study after dosing on Day 1) after the last dose of study drug will be reported and entered in the case report forms (CRFs).

The Medical Dictionary for Regulatory Activities (MedDRA) Version 23.0 will be used to map verbatim AEs to preferred term (PT) and their respective primary system organ class (SOC). However, a different (non-primary) system organ class may be selected where appropriate after a medical review of the mapping.

4.5.2 Clinical Laboratory Assessments

Hematology, coagulation, serum biochemistry, and urinalysis are collected as scheduled in Table 1 through Table 5. The following information will be derived for each of the hematology, coagulation, serum biochemistry, urinalysis, and other parameters:

- Change from baseline at all post-baseline time points
- Classification relative to the normal range ('Low', 'Normal', or 'High')
- Potentially clinically significant (PCS) abnormalities, if applicable

In addition, the following tests will be performed:

- **Serum Pregnancy Test:** Blood samples to assess pregnancy status by beta-human chronic gonadotropin (β-hCG) will be collected from all female subjects according to the schedules summarized in Table 1 and Table 5.
- Estimated glomerular filtration rate: Estimated glomerular filtration rate (eGFR) will be calculated at the Screening Visit using the 4-variable Modification of Diet in Renal Disease Study (MDRD) equation:
 - eGFR (mL/min/1.73 m²) = 175 × Serum Creatinine $^{-1.154}$ × age $^{-0.203}$ × 1.212 (if participant is black) × 0.742 (if female).
- **Viral Serology**: Blood samples to assess Hepatitis B surface antigen (HBsAg), Hepatitis C virus (HCV) antibodies and human immunodeficiency virus (HIV) antibodies will be obtained at the Screening Visit.
- **Drugs of Abuse and Alcohol Screen:** Urine samples to assess amphetamine, barbiturates, benzodiazepine, cannabinoids, cocaine, ethanol, opiate, oxycodone, methadone and methylenedioxymethamphetamines will be obtained according to the schedule summarized in Table 1.
- **Ketone Bodies:** Blood samples to assess ketone bodies (β-hydroxybutyrate and acetoacetate) will be collected according to the schedules summarized in Table 2 through Table 5.

• Urine Calcium, Sodium and Glucose: Urine samples to assess calcium, sodium and glucose will be collected according to the schedules summarized in Table 1 through Table 4.

4.5.3 Vital Signs

Vital sign assessments including systolic and diastolic blood pressure, heart rate, respiratory rate and body temperature (°C) will be performed according to schedules summarized in Table 1 through Table 5. The following information will be derived for all vital signs and body weight:

- Change from baseline at all post-baseline time points
- PCS abnormalities

4.5.4 12-Lead Electrocardiogram

12-lead ECG recordings and conduction intervals including interval from beginning of the QRS complex in the frontal plane to the next QRS complex (RR), interval from beginning of the P wave to the beginning of the QRS complex in the frontal plane (PR), duration of QRS complex in the frontal plane (QRS), interval from beginning of the QRS complex to end of the T wave in the frontal plane (QT) and Fridericia-corrected QT interval (QTcF) will be obtained according to the schedules summaried in Table 1 through Table 5. The following information will be derived for each of the 12-lead ECG measurements:

- Change from baseline at all post-baseline time points
- PCS abnormalities

The overall clinical interpretation of an ECG will be assessed as follows: normal, abnormal not clinically-significant or abnormal clinically-significant.

4.5.5 Physical Examinations

Physical examinations will be performed by a physician or qualified designee according to the schedules summarized in Table 1 through Table 5, and will include examination of the following body systems: general appearance, skin (including hair and nails), HEENT (head, ears, eyes, nose, throat), neck/thyroid, chest/lungs, cardiovascular, gastrointestinal, neurological, psychiatric/emotional, lymphatic and musculoskeletal.

Clinically-significant abnormal physical examination findings will be recorded as medical history or AE where appropriate.

4.5.6 Other Safety Assessments

Height and weight measurements will be performed according to the schedules summarized in Table 1 through Table 5. The BMI will be calculated at the Screening Visit using the following equation: (weight (kg)/[height (m)]²), where the weight in kilograms will be documented to one decimal place and the height in centimeters will be rounded to the nearest whole number.

In addition, the following assessments will be performed according to the schedules summarized in Table 1 through Table 5:

- **Bristol Stool Chart:** Subjects will report their stool pattern to the site staff at three visits (Screening Visit, Day -3 and the Follow-up Visit). During the Admission Period (Day -3 through Day 35), every time a subject has a bowel movement, a member of the site staff will assist the subject in characterizing the stool using the Bristol stool chart (BSC) including documentation of the date and time.
- Coronavirus Disease Test: Respiratory specimens (e.g., nasopharyngeal, oropharyngeal, nasal) will be collected at the Screening Visit and on Day -3 to assess for the presence of severe acute respiratory syndrome coronavirus 2 (SARS-CoV-2) ribonucleic acid that causes COVID-19 using reverse transcription polymerase chain reaction.

5 ANALYSIS POPULATIONS

Randomized Population: All subjects randomized to receive JTT-662 or placebo on Day 1.

Safety Population: All subjects who receive at least one dose of JTT-662 or placebo, including those who do not complete the study. Subjects who were dosed on Day -1 only (placebo run-in) will also be included in the safety population.

Pharmacokinetic Population: All randomized subjects who received at least one dose of JTT-662 starting on Day 1, and have evaluable JTT-662 plasma concentration data. Subjects will be excluded or partially excluded from the statistical analysis of PK parameters if they significantly violated the inclusion or exclusion criteria or deviated significantly from the protocol.

Pharmacodynamic Population: All randomized subjects who received at least one dose of JTT-662 or placebo starting on Day 1, and have evaluable PD data to facilitate the calculation of PD parameters. Subjects will be excluded or partially excluded from the statistical analysis if they significantly violated the inclusion or exclusion criteria or deviated significantly from the protocol.

STATISTICAL METHODS

The statistical analysis will be conducted following the principles specified in the International Council for Harmonisation of Technical Requirements for Pharmaceuticals for Human Use (ICH) Topic E9 Statistical Principles for Clinical Trials (CPMP/ICH/363/96).

No formal inferential test will be performed in this Phase 1 study.

All statistical tabulations and analyses will be performed using Any changes to the analyses described in this plan will be detailed in the CSR.

All results collected in the database will be presented in listings. All continuous data will be listed with the same precision as will be presented in the database. Data listings will be sorted by treatment group, subject ID, and time point.

Unless otherwise noted, continuous variables will be summarized using number of non-missing observations (n), arithmetic mean (mean), standard deviation (SD), median, minimum, and maximum. For PK parameters, summary statistics will also include the coefficient of variation (CV%) and geometric mean (geometric mean will not be presented for t_{max}). For plasma concentrations and PD parameters, summary statistics will also include the CV%. Categorical variables will be summarized using the frequency count and the percentage of subjects in each category.

All subjects randomized to placebo on Day 1 will be included in the placebo treatment group unless otherwise specified.

In the data listings, study day relative to first dose of study drug on Day 1 may be presented. Study day relative to first dose of study drug on Day 1 will be calculated as: event date – first dose date on Day 1 (+ 1 if event date \geq first dose date on Day 1).

Baseline will be the latest non-missing measurement prior to the first dose of study drug on Day 1, unless otherwise specified

For safety summaries, the unscheduled and repeat assessments will not be summarized; however, all results will be included in the data listings.

Disposition, demographics, and baseline characteristics and all categorical safety parameters will be summarized by each treatment group and overall.

6.1 Sample Size

Approximately 36 subjects (3 cohorts, 12 subjects per cohort [9 active: 3 placebo]) will be randomized into this study. The sample size is not statistically determined.

6.2 Subject Disposition

Summaries of analysis populations and subject disposition will be presented by treatment group and overall for the safety population and will contain the following information:

- Number and percent of subjects in each population (safety, randomized, PK, PD)
- Number and percent of subjects who were dosed (safety population)
- Number and percent of subjects who completed the dosing period
- Number and percent of subjects who completed the study including follow-up visit
- Number and percent of subjects who discontinued early and reason for early discontinuation

Subject disposition and analysis populations will be tabulated and presented in listings. Percentage will be calculated based on number of subjects in the safety population. Screen failure reasons will also be summarized and listed.

6.3 Protocol Deviation Reporting

Protocol deviations will be listed.

6.4 Subject Demographics and Baseline Characteristics

Subject demographic data and baseline characteristics will be summarized using descriptive statistics and include the following parameters collected at screening: sex, age, race, ethnicity, height, body weight, BMI, HbA1c and FPG. Demographic data and baseline characteristics will be presented by treatment group and overall for the safety population and also be listed.

6.5 Medical and Surgical History

Medical and surgical history will be coded using the MedDRA (Version 23.0). Medical history data along with the corresponding SOC and PT coded from the MedDRA dictionary will be presented in the data listing.

6.6 Extent of Exposure

Exposure data will be presented in the data listing.

6.7 Pharmacokinetic Analysis

Pharmacokinetic analysis will be performed for JTT-662 for the PK population.

6.7.1 Method of Pharmacokinetic data representation

The PK data including individual data and descriptive statistics for plasma concentrations, PK parameters and the result of PK data analysis will be represented with three significant values except for CV% which will be represented to one decimal place.

All concentration values reported as no results (not collected or not determined) values will be treated as missing. Plasma concentration values that are BLQ will be set to zero for calculation of summary statistics and plotting mean concentration profiles.

6.7.2 Descriptive Statistics of Plasma Concentrations

The plasma concentration data will be summarized by JTT-662 dose levels and nominal time point. Mean and individual plasma concentration-time profiles will be plotted by dose levels on linear and semi-logarithmic scales. Scheduled (nominal) sampling times will be used for all summary tables and plots of plasma concentration data.

6.7.3 Descriptive Statistics of Pharmacokinetic Parameters

The PK parameters will be summarized by JTT-662 dose levels and day for the PK population.

6.7.4 Statistical Analysis of Pharmacokinetic Parameters

Dose proportionality of C_{max} and appropriate AUC values on Day 1 and Day 28 will be assessed for JTT-662. The relationship between each parameter and dose is written as a power function:

Parameter =
$$A*dose^b$$
 (Equation 1)

Where "A" is a constant, "b" is the proportionality constant and "parameter" is the PK parameter of interest (e.g., C_{max} and AUC_{tau}). Each PK parameter will be plotted against dose. The exponent, b, will be estimated by performing linear regression of the (natural) log-transformed parameter on the log-dose, since taking logarithm on both sides of (Equation 1) gives the linear relationship, log parameter = a + b*log dose, where a = log(A). Therefore the exponent, b, is estimated by the slope of the resulting regression line. A value of b close to 1 indicates dose proportionality. Dose proportionality will be assessed descriptively by presenting the estimate of b, its standard error and the 90% confidence interval (CI).

The estimated geometric means at each dose level, the estimate of the slope (b), its 90% and 95% CIs, and model residual error will be obtained from the model. Furthermore, the geometric means based on the raw data and the dose normalized ratio for each pair of doses will be presented. C_{max} and AUC_{tau} will be plotted against dose on the log-scale.

The sample SAS code (with appropriate changes) for calculating the slope of dose proportionality will be:

```
PROC MIXED DATA= DATASET;

MODEL LNPKPARM=LNDOSE /SOLUTION CL ALPHA=0.1*;

ODS OUTPUT SOLUTIONF=SOLUTION1(RENAME= (ESTIMATE=EST STDERR=SE));

RUN;
```

*alpha = 0.05 and 0.1

In addition, a model fit test will be performed by testing the quadratic term in a quadratic regression, and the p-value for the quadratic term will be presented.

The sample SAS code (with appropriate changes) will be used for quadratic regression:

```
PROC GLM DATA= DATASET;
      MODEL LNPKPARM=LNDOSE LNDOSE*LNDOSE/SOLUTION CL ALPHA=0.1;
RUN;
```

6.8 Pharmacodynamic Analysis

Observed values and change from baseline of PPG concentrations will be summarized by treatment group and time point in terms of the number of subjects, arithmetic mean, SD, CV%, median, minimum and maximum. Baseline for PPG concentrations will be the pre-dose (Hour 0) value of the PPG profile on each PPG collection day. Concentrations will be listed, mean and individual plots will also be presented.

The plasma glucose excursion defined as the maximum glucose value observed after breakfast (0-4 hours after breakfast) minus the pre-dose (Hour 0) value will also be summarized for observed values and change from baseline on Days -1, 1, 14 and 28. Day -1 will be baseline.

Area under the observed effect-time curve from the time of starting breakfast until the 4-hour time point (AUEC₀₋₄) will be calculated for PPG on Days -1, 1, 14 and 28 for the PD population. Observed values and change from baseline of AUEC₀₋₄ will be summarized descriptively. Baseline will be the corresponding parameter value on Day -1.

A linear mixed effect model including day as the fixed effect and subject as the random effect will be fitted on the the PD parameter for each treatment group separately. The difference of the least square means of AUEC₀₋₄ between the compared days (Day 1 vs. Day -1, Day 14 vs. Day -1, Day 28 vs. Day -1 and Day 28 vs. Day 14) and the 90% and 95% CIs of the least square mean difference will be calculated.

The following sample SAS code may be used, with appropriate changes, for the analysis:

```
PROC MIXED DATA=DATASET;
BY TREATMENT:
  CLASS SUBJID DAY;
  MODEL PDPARVAL = DAY / DDFM=KR;
  RANDOM SUBJID;
  LSMEANS DAY / CL;
  ESTIMATE 'Day 1 Vs. Day -1' Day 1 0 0 -1/ALPHA = 0.05 CL;
  ESTIMATE 'Day 14 Vs. Day -1' Day 0 1 0 -1/ALPHA = 0.05 CL;
  ESTIMATE 'Day 28 Vs. Day -1 ' Day 0 0 1 -1/ALPHA = 0.05 CL;
  ESTIMATE 'Day 28 Vs. Day 14 'Day 0 -1 1 0/ALPHA = 0.05 CL;
  ESTIMATE 'Day 1 Vs. Day -1' Day 1 0 0 -1/ALPHA = 0.1 CL;
  ESTIMATE 'Day 14 Vs. Day -1' Day 0 1 0 -1/ALPHA = 0.1 CL;
  ESTIMATE 'Day 28 Vs. Day -1 ' Day 0 0 1 -1/ALPHA = 0.1 CL;
  ESTIMATE 'Day 28 Vs. Day 14 ' Day 0 -1 1 0/ALPHA = 0.1 CL;
 RUN;
```

[figure not shown]
Statistical Analysis Plan - Protocol No. AT662-U-20-003

Additionally, the change from baseline (Day -1) of AUEC₀₋₄ will be analyzed using the mixed effect model with repeated measures (MMRM). The model will include fixed effects for treatment, day, and treatment by day interaction, subject as repeated measures and baseline value as a covariate. The difference of the least squares means between each JTT-662 dose group relative to placebo at the same day will be estimated, along with two-sided 90% and 95% CIs and p-values. Least squares means will also be presented.

[figure not shown]
The following sample SAS code may be used, with appropriate changes, for the analysis:

```
PROC MIXED DATA=DATASET;
 CLASS DAY TREATMENT;
 MODEL CHG = DAY TREATMENT DAY*TREATMENT BASELINE / DDFM=KR;
 REPEATED /SUBJECT=SUBJECT(TREATMENT) TYPE=UN*;
 LSMEANS DAY*TREATMENT /PDIFF CL ALPHA=0.1**;
RUN:
```

^{**} alpha = 0.05 and 0.1.

^{*} Other covariance structure will be used if UN leads to non-convergence of the model.

Statistical Analysis Plan - Protocol No. AT662-U-20-003

6.10 **Analysis of Safety Data**

Safety analyses will be conducted on the Safety Population and will be performed for all safety variables specified below.

The safety evaluation will include AEs, clinical safety laboratory tests (e.g., hematology, serum biochemistry, coagulation, urinalysis), vital signs, 12-lead ECGs, BSC findings, ketone bodies, urinary calcium excretion from the time of dosing until the 24-hour time point (UCE₀₋₂₄) and urinary sodium excretion from the time of dosing until the 24-hour time point (UNa E_{0-24}) and UGE $_{0-24}$.

Observed and change from baseline of vital signs, ECG parameters and clinical laboratory data will be presented in tabular form with arithmetic mean, SD, median, minimum and maximum, or in frequency tabulation form as appropriate. For the laboratory safety data, out of range values and PCS abnormalities will be flagged in the data listings.

Potentially clinically significant abnormalities will be defined according to the Akros Safety Reporting Standards Potentially clinically significant values for vital signs, ECG, and laboratory data will be flagged in data listings.

Treatment-emergent PCS values will be summarized, presenting the number and percentage of subjects who had at least one PCS value after study drug administration on Day 1. The denominator is always the number of subjects in the safety population, regardless of whether the subject had any post-baseline measurements. The numerator is any PCS value in the treatment-emergent period if the baseline is normal or missing; and is any worsening PCS value in the treatment-emergent period if the baseline is also a PCS value.

A worsening PCS is defined as a > (<) 0 change from baseline if a high (low) value indicating undesirable outcome; or the PCS value is in the opposite direction of the baseline PCS value.

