6.10.1 Adverse Events

Adverse events will be coded using the MedDRA (Version 23.0) and will be summarized by SOC and PT.

A treatment-emergent adverse event (TEAE) is defined as any AE with an onset date/time at or after the placebo dosing on Day -1. A pre-treatment AE is defined as any AE with an onset date before the placebo dosing on Day -1.

The summary of TEAEs will be presented for the following groups:

- Placebo run-in: including AEs with onset between the placebo dosing on Day -1 and before dosing on Day 1 for all subjects in the safety population.
- Placebo treatment group: including AEs with onset at or after the placebo dosing on Day 1 for the subjects who are randomized to placebo on Day 1.
- JTT-662 5 mg: including AEs with onset at or after the JTT-662 5 mg dosing on Day 1 for the subjects who are randomized to JTT-662 5 mg on Day 1.

- JTT-662 10 mg: including AEs with onset at or after the JTT-662 10 mg dosing on Day 1 for the subjects who are randomized to JTT-662 10 mg on Day 1.
- JTT-662 XX mg (XX represents JTT-662 dose level for Cohort 3): including AEs with onset at or after the JTT-662 XX mg dosing on Day 1 for the subjects who are randomized to JTT-662 XX mg on Day 1.

The overall incidence of TEAEs (number and percentage of subjects) as well as the number of events will be summarized for each treatment group.

Summaries of TEAEs will include the following: Incidence of TEAEs (overview including number and percentage of participants with any TEAEs, serious TEAEs, discontinuations due to TEAEs, drug-related TEAEs, severe TEAEs, all deaths (AEs leading to death regardless of treatment emergence) and TEAEs leading to death; event counts will also be included).

The TEAEs will be summarized by SOC, PT, and treatment group using frequency counts and percentages (number and percentage of subjects with an event). Each subject may only contribute once to each of the incidence rates, regardless of the number of occurrences. In addition, the following summaries will be performed for the summary groups as described above:

- TEAEs by SOC, PT
- TEAEs by SOC, PT and maximum reported severity
- TEAEs by SOC, PT and causality
- TEAEs by PT (in order of descending frequency in the total JTT-662 group).
- Serious Adverse Events (SAE) by SOC, and PT

Listings of AEs, SAEs, AEs leading to study discontinuation will also be presented. The AEs with onset in the placebo run-in period will be flagged in the listings.

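### The sample ESTIMATE statements for within-group AUEC0-4 are right only if Day -1 is the last DAY level, an order the SAP does not state and the usual ascending sort does not give

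*SAP*

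**What the plan says.** SAP 6.8 fits a linear mixed model to AUEC0-4 separately in each treatment group, with day as the fixed effect and subject as the random effect. The days are -1, 1, 14 and 28, and Day -1 is the baseline. The planned differences in least squares means are "Day 1 vs. Day -1, Day 14 vs. Day -1, Day 28 vs. Day -1 and Day 28 vs. Day 14", each with 90% and 95% confidence intervals.

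The code that follows is introduced with "The following sample SAS code may be used, with appropriate changes, for the analysis". It declares "CLASS SUBJID DAY" and requests "LSMEANS DAY / CL". It then has eight ESTIMATE statements, four labels at each of two alpha levels. The first is "ESTIMATE 'Day 1 Vs. Day -1' Day 1 0 0 -1/ALPHA = 0.05 CL" and the last is "ESTIMATE 'Day 28 Vs. Day 14 ' Day 0 -1 1 0/ALPHA = 0.1 CL". Both alpha levels use the same coefficients. Neither the code nor the surrounding text gives an `ORDER=` option, a format, a recode or a statement of the order of the DAY levels.

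The later MMRM code in the same section uses "REPEATED /SUBJECT=SUBJECT(TREATMENT) TYPE=UN" and names no DAY effect in that statement.

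**The concern.** ESTIMATE coefficients are read by position, so a label is true only if the levels sit in the positions its author had in mind. Here every contrast against baseline puts its -1 coefficient in the fourth place. That treats Day -1 as the last level, although it is the smallest day number and the earliest in time.

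These statements produce the planned within-dose change in postprandial glucose. An error would also be quiet. Each vector sums to zero and is a valid difference between two days, so the model would run normally. With a random subject effect and complete data, every pairwise day difference has the same standard error, so the interval widths would look normal too.

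**Working it through.** **Inputs (all from SAP 6.8).** The DAY levels are -1, 1, 14 and 28. The four labels and their coefficients are:

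| Label | Coefficients by position |
|---|---|
| A: Day 1 against Day -1 | (1, 0, 0, -1) |
| B: Day 14 against Day -1 | (0, 1, 0, -1) |
| C: Day 28 against Day -1 | (0, 0, 1, -1) |
| D: Day 28 against Day 14 | (0, -1, 1, 0) |

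**Step 1: the order the code needs.** A requires position 1 = Day 1 and position 4 = Day -1. B requires position 2 = Day 14. C requires position 3 = Day 28. Under that order D is position 3 minus position 2 = Day 28 minus Day 14, which is also correct. The labels are therefore reproduced under (1, 14, 28, -1). Checking all 4! = 24 orders gives 1 order with four labels right, 4 orders with exactly one right, and 19 with none right. Putting Day -1 last is necessary but not sufficient: (1, 28, 14, -1) gets only A right.

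**Step 2: the order likely to occur.** The documents do not state the software's sorting rule. The assumption is that, without `ORDER=`, CLASS levels sort in ascending order of value or text.

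| Coding of DAY | Resulting order | Labels right |
|---|---|---|
| Numeric; text -1; text Day -1; text Baseline; chronological visit number | (-1, 1, 14, 28) | 0 of 4 |
| Right-justified text | (1, -1, 14, 28) | 0 of 4 |
| Text Placebo run-in, beside Day 1, Day 14 and Day 28 | (1, 14, 28, -1) | 4 of 4 |

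SAP 6.10.1 does use the last name, in "Placebo run-in: including AEs with onset between the placebo dosing on Day -1", but only to group adverse events. SAP 6.8 calls the day Day -1 throughout.

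**Step 3: what the labels return under (-1, 1, 14, 28).** Let d1, d14 and d28 be the true changes from Day -1, so that Day -1 itself has change 0.

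| Label | Intended | Returned |
|---|---|---|
| A | d1 | Day -1 minus Day 28 = -d28 |
| B | d14 | Day 1 minus Day 28 = d1 - d28 |
| C | d28 | Day 14 minus Day 28 = d14 - d28 |
| D | d28 - d14 | Day 14 minus Day 1 = d14 - d1 |

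**Step 4: size.** For a constant effect d1 = d14 = d28 = d, the four labels return -d, 0, 0 and 0 instead of d, d, d and 0. The examples below use assumed effects in mg*h/dL, because the documents give none.

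| Assumed (d1, d14, d28) | A, B, C should be | A, B, C returned |
|---|---|---|
| Constant, -50 | -50, -50, -50 | +50, 0, 0 |
| Constant, -300 | -300, -300, -300 | +300, 0, 0 |
| Waning (-200, -150, -100) | -200, -150, -100 | +100, -100, -50 |
| Growing (-100, -150, -200) | -100, -150, -200 | +200, +100, +50 |

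D comes out numerically correct in these examples only because the assumed steps are equal: Day 14 minus Day 1 happens to equal Day 28 minus Day 14.

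**Step 5: the replacement.** Under (-1, 1, 14, 28), (-1 1 0 0) gives d1, (-1 0 1 0) gives d14, (-1 0 0 1) gives d28 and (0 0 -1 1) gives d28 - d14. All four labels are then true.

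**Secondary check, MMRM code.** The change-from-baseline records are Days 1, 14 and 28. If REPEATED names no DAY effect, records take their place in the unstructured matrix by sequence. A subject with Day 28 but no Day 14 would have the Day 28 record treated as the second occasion. This arises only when an earlier day is missing and a later one is present. The treatment comparisons there come from LSMEANS, so they do not share the contrast-order error.

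**The case against.** The strongest reply is that the plan itself is right and only an illustration is in question. The prose defines the comparisons correctly, and the code is expressly open to adaptation. All eight statements agree with one order, which suggests the author had Day -1 last in mind and did not write it down. The failure depends on how DAY is coded and on a sorting rule, neither of which the documents give. The public text also has gaps, so the absence of a coding note can be asserted only for what is visible.

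Several outputs would expose an error: LSMEANS by day from the same step, the descriptive summary of change from Day -1 in SAP 6.8 (whose mean equals the within-group difference when data are complete), and the MMRM least squares means. Protocol 3.10 also calls for statistical quality control. Finally, this is a Phase 1 study whose sample size is not statistically determined, the SAP disclaims formal inferential testing, and the placebo-controlled comparison comes from the MMRM.

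Much of this stands. It makes a reported sign reversal less likely and limits the severity. It does not show that the printed statements return what their labels say when the days carry the values SAP 6.8 gives them. Nothing tells the programmer that level order is one of the changes needed. The secondary MMRM point is narrow, because subjects stay in-house through Day 35 and ordinary dropout would not trigger it.

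**Conclusion.** The sample code is wrong as written for the natural day values, and it should be corrected. That the labels require the order (1, 14, 28, -1) is certain and needs no assumption. That the ascending order defeats all four labels is equally certain as algebra. That this order would actually arise rests on two assumptions: DAY is coded with its day numbers or an equivalent, and CLASS levels sort ascending by default.

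If so, all eight ESTIMATE statements are affected. The label for Day 1 against baseline returns the Day 28 change with its sign reversed, and the other two baseline labels no longer measure change from baseline. The numerical examples depend on assumed effects, but the mismatch between label and contrast does not. The prose comparisons, the LSMEANS output and the MMRM treatment contrasts are unaffected.

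**What to change.** In the SAP 6.8 sample code, write the coefficients for the order (-1, 1, 14, 28), at both alpha levels:

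- Day 1 against Day -1: `-1 1 0 0`
- Day 14 against Day -1: `-1 0 1 0`
- Day 28 against Day -1: `-1 0 0 1`
- Day 28 against Day 14: `0 0 -1 1`

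Alternatively, take the differences from LSMEANS, use LSMESTIMATE keyed by level value, or keep the coefficients and state that DAY is ordered 1, 14, 28, -1 and how that is enforced.

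As a secondary edit to the MMRM code, add SUBJECT to the CLASS statement and write `REPEATED DAY / SUBJECT=SUBJECT(TREATMENT) TYPE=UN`.

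The cost is a few lines of SAP text before programming. Data collection and the planned comparisons do not change.
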